12.4.1 Primary outcome

Physical function and pain interference, as measured with the Patient Reported Outcome Measurement System (PROMIS) computer adaptive tests (CATs) are the co-primary outcomes. The CATs in the Mayo Clinic Epic EHR have been parameterized with stopping rules based on number of items administered rather than a standard error of measurement-defined threshold. IRT-based instruments have generally better discrimination across the entire trait range than legacy PROMs,^{19,20} and CAT administration enhances measurement efficiency and precision.^{21,22} The PROMIS item banks have been validated in the target populations.²³⁻²⁵ The PROMIS physical function and pain interference CATs will be assigned via an automated Epic function precisely 3 months following each patient's surgery. Patients will receive an automated reminder message via their patient portals prompting them to complete the PROMs.

Because post-operative visit requirements and sequences vary across surgical practices, administration of the PROMIS CATs will not be linked to a specific visit, but rather assigned automatically after 3 months have elapsed since surgery. If this data coincides with a clinic visit, then patients will be encouraged to complete the PROMIS CATs via the Epic Welcome interface using a tablet in the waiting room prior to their clinic visit.

12.4.2 Secondary outcomes

Secondary outcome measures will include opioid consumption, NPPC use, healthcare utilization and anxiety. Anxiety will be measured in a manner similar to physical function and pain interference with a PROMIS CAT administered via the Epic MyChart portal or the Welcome tablet interface prior to a clinic visit that coincides with the 3-month post-surgical time point.

Opioid consumption will be collected using three methods. First, opioid consumption per hospital day, will be extracted from the medication administration log in the EHR. As in previous work,²⁶⁻²⁸ parenteral, transdermal, and oral opioid consumption will be expressed as oral morphine equivalents (OMEs). Second, oral and transdermal opioids prescribed by a Mayo Clinic provider at the time of hospital discharge and during the interval between hospital dismissal and the 3 month post-surgical assessment point will be extracted from the EHR and converted to OMEs. Last, because outpatient prescriptions do not accurately capture opioid consumption, patients will be queried at the 3 month post-operative time point regarding their opioid use using a subscale from a validated opioid consumption questionnaire.²⁸

NPPC use will be collected using two methods. First, the frequency with which patients use specific NPPCs during their hospital stays will be

extracted from Epic flowsheets. Nurses, as well as occupational and physical therapists record delivery of modalities as well as education regarding modalities in Epic flowsheets. This information will be electronically extracted and expressed as count data. Second, patients' use of NPPC modalities will be assessed using self-report. At the 1-, 2- and 3-month assessment point patients will be queried regarding which of the NOHARM NPPC modalities they have used since hospital discharge. The will be presented with a list of the NOHARM modalities and asked to indicate those that they have used. Epic cascading logic will then present a second item for each modality that a patient has used which will ask them "How many times per week, on average, do you use *modality*?" Healthcare utilization for NOHARM will consider hospitalizations, post-acute care, ED visits, surgery clinic outpatient visits, and calls to the surgery care team and post-acute care (PAC). EHR entries and administrative billing data will be aggregated to construct a comprehensive data set of all clinical encounters. Data collected for hospitalizations will include procedures and admission and discharge diagnoses. For ED encounters, we will capture diagnoses and procedures. Clinic visits will be captured using billing data which will include CPT codes, ICD-10 codes, location, and clinician NPI numbers.

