7.3 Study Enrollment Procedures

All eligible patients at participating sites will be enrolled in this minimal risk, population-based study. An automated EHR-based algorithm will identify patients meeting inclusion criteria for the NOHARM study based on age, surgical procedure, clinical department, and location.

Eligible patients in not-yet activated clusters will receive usual care; data collected from this group will serve as “control” data in this stepped wedge study. Control state data will be collected prior to cluster activation.

All patients scheduled for surgery; as well as their care surgical teams, physical and occupational therapists, and unit nurses, in activated practice clusters will be exposed to the intervention per the randomization scheme. Because the intervention is embedded in the EHR, patients who are unable to interact with the portal-based Healing After Surgery Guide will not provide the data needed to populate and drive the EHR-based algorithms and clinical decision support tools. Therefore, these individuals will be less exposed to the intervention. However, the patients who do not interact with the Healing after Surgery Guide via the EHR patient portal prior to their hospital admission¹ will have the opportunity to select NPPC modalities during their hospitalization, both pre- and post-operatively. By communicating their NPPC selections to their unit nurses, their preferences will be entered into the EHR via flowsheets. Subsequently, all EHR clinical decision support functionalities to encourage NPPC use will be operational for these patients. Cognitive limitations, lack of English fluency, or psychiatric illness may result in an inability to use the Healing After Surgery Guide which may also result in reduced exposure to the intervention.

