Additionally, patients' NPPC selection will be visible to clinical providers on the Epic inpatient Summary view. These components are considered standard of care.

Mayo Education Material:

A suite of self-management educational materials will be available to support patients' use of NPPC modalities and to help them trouble shoot and refine the use of their selected modalities. These print materials and videos provide information

and instruction on the safe and appropriate use of NPPC strategies for addressing post-surgical, post-acute pain. The materials additionally clarify how patients may adapt NPPC modalities to derive optimal benefit given their unique requirements and post-surgical precautions. All education materials have been developed, vetted and approved through Mayo Clinic's Office of Patient Education processes and reflect existing standard of care for patient education. These materials will be available to patients via the Healing After Surgery website (healingaftersurgery.mayoclinic.org) and on Mayo Clinic Television. Brief video descriptions of the NPPC modalities are imbedded in the Healing After Surgery Guide. The materials include video and print resources, with the latter being available in both electronic and paper formats. The materials offer informational, instructional, and guided experiential content for all NOHARM NPPC modalities, as appropriate. A Healing After Surgery Workbook is also available. The workbook offers patients a location to record their experiences, concerns, and successes, as well as providing motivational messages.

Patients may view the self-management educational materials during their hospital stays on Mayo Clinic television. Based on patients' NPPC modality selections, inpatient nurses will be prompted to show patients how to navigate to the materials on Mayo Television, familiarize them with the Healing After Surgery website, and provide them with print materials if desired. Nurses will also use the educational materials to discuss pain management planning with patients to refine their management plans following hospital dismissal.

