 - [PACU](#)
 - [PT](#)
 - [Surgeons APP resident](#)
- [RN Education points helps RNs provide NOHARM education to patients](#)
- RN Task/Brain/worklist: NOHARM tasks the RN has to complete
- NOHARM Banner: the NOHARM banner is pink to help with awareness
- [RN Orders \(search folder for Orders for all the files\)](#)
- Best Practice Alerts: alert Mayo Clinic care teams about key steps to take for NOHARM. Triggered off of certain Epic event
 - PT/OT BPA
 - Pain > 1 BPA
 - Opioid Rx BPA

Trial Coordination

- [NOHARM Data and Safety Monitoring Board \(DSMB\) Charter](#)
- [NOHARM Data and Safety Monitoring Plan \(DSMP\)](#)
- [Letters of Support](#)

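### The in-hospital NPPC use count (12.4.2) draws on staff flowsheets that record education as well as delivery, so it can rise at activation without more patient use

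*Combined protocol and SAP*

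**What the plan says.** Section 12.4.2 lists the secondary outcomes: "Secondary outcome measures will include opioid consumption, NPPC use, healthcare utilization and anxiety". NPPC use has two sources. For the first, "the frequency with which patients use specific NPPCs during their hospital stays will be" taken from Epic flowsheets. The plan then describes what those flowsheets hold: "Nurses, as well as occupational and physical therapists record delivery of modalities as well as education regarding modalities in Epic flowsheets". It goes on: "This information will be electronically extracted and expressed as count data". The second source is patient self-report at 1, 2 and 3 months, about use since discharge.

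Other sections describe what changes for staff when a cluster is activated:

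- **8.1:** stored selections steer the education that unit nurses give, and "inpatient nurses will be prompted to show patients how to navigate to the materials on Mayo Television".
- **7.3:** for patients who did not use the portal guide before admission, "By communicating their NPPC selections to their unit nurses, their preferences will be entered into the EHR via flowsheets".
- **Appendix B:** the care-team components include "RN Task/Brain/worklist: NOHARM tasks the RN has to complete", a banner, RN orders, role-based training and best practice alerts, one of them for PT/OT.
- **16.1:** documentation is among the components of the trial's EHR build.

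Section 12.5 has a general statement that primary and secondary outcomes will be compared between groups with mixed models. Its only NPPC model, model (2), uses the 3-month binary items summed over 14 modalities.

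**The concern.** The stated construct is something the patient does, but the source is something staff write down, and part of what they write down is teaching. Being taught about a modality is not using it. Because the intervention steers and prompts that teaching, a count that includes education entries partly scores delivery of the intervention as its own effect.

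The recorders are also the people the intervention is aimed at. If tasks, alerts and training lead nurses and therapists to chart the same bedside activity more fully, the count moves again with no change in use. Any such shift starts at activation, so it coincides with the intervention indicator. Randomization of the clusters and the calendar-time term do not remove it.

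At stake is a secondary result that could be reported as greater in-hospital use of NPPC, an early step in the trial's rationale. It could also enter 12.7.2, which allows interim patient measures as mediators without naming them.

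**Working it through.** The plan states no figure for this outcome, so there is nothing to reproduce. The check has two parts.

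**1. The text, side by side**

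| Question | What the documents give |
|---|---|
| What is to be measured? | How often patients use specific modalities in hospital (12.4.2) |
| What is recorded? | Delivery and education, by nurses and therapists (12.4.2) |
| Is there a rule to separate them? | None; the information as a whole is turned into counts (12.4.2) |
| Does activation change education? | Yes; selections direct it and nurses are prompted (8.1) |
| Does activation change charting of delivery? | Not stated; it can be inferred from 7.3, 16.1 and Appendix B |
| Is there a safeguard? | The 13.3.2 audit checks extraction, on 2-5% of patients in the most recently activated clusters; no control-period charts are named |
| Is there blinded review? | Only for deciding which stays count as hospitalizations (12.4) |
| How is the count analysed? | Under the general statement in 12.5; it has no model of its own |

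**2. Illustration of size**

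Every entry rate and completeness value here is an assumption.

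*Education counted, delivery unchanged.* Let d be delivery entries per stay, and e0 and e1 the education entries before and after activation. The apparent rate ratio is (d + e1)/(d + e0).

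- d = 3, education 0 to 1: 4/3 = 1.33
- d = 3, education 0.5 to 1.5: 4.5/3.5 = 1.29
- d = 3, education 0 to 3: 6/3 = 2.00
- Lowest and highest values tried: d = 5, education 0 to 0.5, 5.5/5 = 1.10; d = 1, education 0 to 3, 4/1 = 4.00

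*Only charting completeness changes.* With completeness c0 before and c1 after, the ratio is c1/c0.

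- 0.9/0.8 = 1.125
- 0.9/0.6 = 1.50
- 0.8/0.4 = 2.00

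*Effect of a filter.* With education entries excluded, the first ratio becomes d/d = 1.00. The second stays at c1/c0, so a filter removes the first source of distortion and leaves the second.

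*Would a small artefact be noticed?* Section 12.2 gives a detectable effect of 0.048 to 0.055 SD for the pain score. If that carried over to a count with mean 3 and Poisson variance (SD = √3 = 1.732), it would be 0.048 × 1.732 = 0.083 to 0.055 × 1.732 = 0.095 entries. That is one extra entry per 10 to 12 patients. With variance three times the mean (SD = √9 = 3), it would be 0.144 to 0.165 entries, or one per 6 to 7 patients. The carry-over is itself an assumption, because the plan gives neither an ICC nor a variance for this count.

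**The case against.** The strongest reply is that the plan's specified NPPC analysis does not use this count. Model (2) in 12.5 and both NPPC hypotheses in 12.6.2 and 12.6.3 rest on 3-month self-report. NPPC use is also absent from the secondary objectives in 1.2 and 4.2. All of this stands and limits the consequence. The count is still a named secondary measure under a general promise of comparison, with no stated model.

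A reader might infer that a positive difference is almost assured and always flatters the intervention. The documents do not support that:

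- They do not say that delivery and education entries are added into one number; separate counts would also fit the text.
- They intend real delivery to increase: staff are to offer preferred modalities (9.2.2) and the trial buys TENS units (Appendix B), so part of a rise may be genuine.
- Self-administered practice may go uncharted, which could understate use in activated clusters.

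A reader might also infer that the prompts instruct staff to complete the flowsheet rows for delivery. No section says so. Section 8.1 prompts nurses to show materials, Appendix B lists a worklist without its contents, and 7.3 concerns preference entries for some patients. More complete charting is a reasonable inference, but it is not a stated fact.

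Finally, self-report cannot stand in for the flowsheet count. It asks about use since discharge, and it comes from patients who have been taught and messaged about the modalities.

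**Conclusion.** The point holds in a limited form. As written, 12.4.2 labels as patient use a count whose source includes education that the intervention directs and prompts. It gives no rule to separate the two, and no safeguard would show a charting difference between control and activated periods. The count can therefore rise at activation without more patient use, and the plan offers no way to tell an artefact from a real increase.

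The size is unknown. Under the assumed inputs the apparent ratio runs from 1.10 to 4.00 if education is counted, and from 1.125 to 2.00 if only charting completeness changes. These ranges show how the mechanism works and do not estimate its likely size. The first depends on education entries entering the count, which the text permits but does not state. The second depends on fuller charting after activation, which is inferred.

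It would be wrong to read this as a threat to the trial's main conclusions. The co-primary PROMIS outcomes, the modelled 3-month NPPC score and the NPPC subgroup hypotheses do not use flowsheet entries. The change is still worth making, because it is cheap and prevents a misleading secondary claim.

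**What to change.** In 12.4.2:

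- Define in-hospital NPPC use as flowsheet entries for delivery or use of a modality only. Exclude education and preference-selection entries and report them separately as intervention fidelity.
- State that a difference in the delivery count between conditions may partly reflect charting.
- Classify the count as a descriptive process measure, which also settles its missing model in 12.5.

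In 12.7.2, state that the count will not be used as a mediator. In the analysis and reporting text, limit claims from self-report to use after discharge.

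Two additions would help if capacity allows: state whether the same flowsheet rows and recording practice applied before activation, and extend the 13.3.2 audit to control-period charts.

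The cost is a wording change, a filter on flowsheet row type, and one secondary measure that becomes descriptive. The optional audit extension would add chart-review work.

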12.5 Data Analyses

Because patients are randomized in clusters, all statistical methods will account for potential correlation of measures within clusters. Such methods include cluster adjusted standard errors for t-tests and χ^2 -tests, and mixed effects models. Patient characteristics will be summarized by intervention status, and tested for difference between intervention groups; any factors which are imbalanced will be accounted for in the main analyses. Factors assessed for balance and potential inclusion in pre-specified analyses are those listed in Section 13.1.1 and all baseline measures listed in 13.1.2.

The primary and secondary outcomes will be compared between intervention groups using mixed effects generalized linear models. Each model will include an indicator for intervention group; a random intercept for cluster; cluster level factors that were used to constrain randomization; calendar time; surgery type; and any patient factors that were imbalanced across groups.

The model details for each outcome are as follows:

1. PROMIS CATs (anxiety (1°), physical function (1°), pain (1°)). These are continuous measures, collected at two time points, pre-operative and 3 months post-operative. To assess the impact of the intervention on these we will estimate three separate models. If Y_{ijt} is the measure at time $t=1,2$ of the i th patient treated by the j th cluster, then we will estimate

$$Y_{ij2} = \beta_0 + \beta_I I_{ij} + \beta_B Y_{ijo} + \beta_T T + \mathbf{B}_X \mathbf{X}_{ij} + \mathbf{B}_Z \mathbf{Z}_j + u_j + e_{ij} \quad (1)$$

where I_{ij} indicates the intervention status, T is calendar time, $u_j \sim N(0, \tau^2)$ is a cluster level random effect, X_{ij} is a vector of patient characteristics, including surgery type, Z_j is a vector of cluster characteristics used for randomization, and e_{ij} is a residual error. By testing $\beta_I = 0$ we can assess whether the intervention is associated with changes in the corresponding measure.

2. NPPC use. This is collected as a binary value for each of 14 modalities, collected at one time point, 3 months post-operative. We will sum these to create a score, and use a model similar to (1) but without a baseline value Y_{ij0} :

$$Y_{ij} = \beta_0 + \beta_I I_{ij} + \beta_T T + \mathbf{B}_X \mathbf{X}_{ij} + \mathbf{B}_Z \mathbf{Z}_j + u_j + e_{ij} \quad (2)$$

Again by testing $\beta_I = 0$ we can assess whether the intervention is associated with changes in the corresponding measure.

3. Opioid use will be measured using 4 outcomes:

- a. Hospital-based consumption, daily oral morphine equivalents (OMEs). This is a continuous measure for each day of hospitalization; we will assume that this depends in part on the day post surgery, D_{ij} and model

$$Y_{ij} = \beta_0 + \beta_I I_{ij} + \beta_D D_{ij} + \beta_T T + \mathbf{B}_X \mathbf{X}_{ij} + \mathbf{B}_Z \mathbf{Z}_j + u_j + e_{ij} \quad (3)$$

For this model we will consider D_{ij} as first continuous and then as categorical.

- b. Discharge and post-discharge prescriptions, daily oral morphine equivalents (OMEs). For this outcome, we will use a model analogous to (3), where D_{ij} is replaced by number of days post discharge.
- c. Number of post-discharge prescriptions. These are counts for the 3 month period following surgery. The impact of the intervention will be assessed using a model similar to (2) but with a Poisson link function:

$$\ln(E(Y_{ij})) \sim \beta_0 + \beta_I I_{ij} + \beta_T T + \mathbf{B}_X \mathbf{X}_{ij} + \mathbf{B}_Z \mathbf{Z}_j + u_j + e_{ij} \quad (4)$$

$$Y_{ij} \sim \text{Poisson}(\mu)$$

We will assess the distribution first using an empty model, and potentially adopt a zero inflated Poisson, negative binomial, or zero inflated negative binomial according to the corresponding AIC values.

- d. Daily use of opioids; this is binary outcome collected one time, at 3 months post-surgery. To assess the impact of the intervention we will use a model similar to (4) but with a logit link:

$$\text{logit}(Y_{ij}) \sim \beta_0 + \beta_1 I_{ij} + \beta_2 T + \mathbf{B}_X \mathbf{X}_{ij} + \mathbf{B}_Z \mathbf{Z}_j + u_j + e_{ij} \quad (5)$$

For a-d we can again test $\beta_1 = 0$ we can assess whether the intervention is associated with changes in the corresponding measure.

4. Healthcare utilization

- a. Hospitalizations
- b. ER visits
- c. Calls to surgical practice

All three of these are count outcomes, and so we will assess the impact of the intervention using a model similar to (4) above. As with (4), we will compare model specifications using an empty model first to determine the best count family (Poisson, negative binomial, zero inflated or not) using AIC, then apply that in the final model.

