13.1.1 Clinical and Demographic variables

- Age
- Sex
- Race/ethnicity
- Insurance status
- Procedure
- Zip code of residence (for classification as rural or non-rural residence)
- Comorbidities
 - Elixhauser comorbidity index

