13.1.2 Treatment and outcomes variables

The following items will be captured in addition to clinical and demographic variables:

- Patient Reported Medical Information System (PROMIS) computer adaptive test (CAT)
 - Pain interference @ baseline and 1, 2 and 3-months post-surgery
 - Physical functioning @ baseline and 1, 2 and 3-months post-surgery
 - Anxiety @ baseline 3 months post surgery
 - Numerical rating scale pain scores reported q shift during hospitalization
- Pain catastrophizing scale
- TAPS prescription medication use item
- PHQ-4 (four item patient health questionnaire for anxiety (GAD 2) and depression (PHQ 2))
- Opioid prescribing survey
- History of opioids prescribed in one year prior to surgical procedure
- In-hospital administration of medications including oral morphine equivalents and opioid alternatives (i.g., acetaminophen) consumed during

hospitalization

- “Discharge” opioid prescriptions, which may be prescribed prior to the procedure due to clinic workflow
- Opioid prescription orders up to 1 year post-discharge (“refills”)

Data will be programmatically extracted and curated by study team members, including data managers, analysts, and/or statisticians. All data will exist prior to the time of access, and no further patient contact is needed for the above data points.

Once extracted from the EHR, data will be maintained on secure, encrypted, password protected research servers at Mayo Clinic. Access to data files will be restricted to individuals listed in the protocol approved by the Mayo Clinic IRB.

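### Section 12.5 picks its additional patient-level covariates by testing for imbalance, with no stated threshold, where a fixed list of pre-exposure prognostic covariates would serve better

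*Combined protocol and SAP*

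**What the plan says.** Section 12.5 (Data Analyses) gives the rule twice. First: "Patient characteristics will be summarized by intervention status, and tested for difference between intervention groups", after which "any factors which are imbalanced will be accounted for in the main analyses". Then, for the models of all primary and secondary outcomes, the terms besides the intervention indicator and the random cluster intercept are "cluster level factors that were used to constrain randomization; calendar time; surgery type; and any patient factors that were imbalanced across groups".

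The pool of candidates is named in advance: "Factors assessed for balance and potential inclusion in pre-specified analyses are those listed in Section 13.1.1 and all baseline measures listed in 13.1.2". In model (1), which serves the co-primary PROMIS outcomes, the patient vector "is a vector of patient characteristics, including surgery type", and the outcome's own baseline score is a separate fixed term.

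The documents give no significance level, no cut-off for a standardised difference, and no fixed list of patient covariates beyond surgery type and, in model (1), the baseline score. Age, sex, race/ethnicity, insurance, rural residence, the "Elixhauser comorbidity index" (13.1.1) and "History of opioids prescribed in one year prior to surgical procedure" (13.1.2) enter only if they are judged imbalanced.

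**The concern.** A test of balance asks whether a covariate differs between groups. It does not ask whether the covariate predicts the outcome, nor whether it confounds the contrast being estimated. Three consequences follow.

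- **Wrong contrast.** In this stepped wedge, with a cluster intercept and calendar time in the model, the intervention coefficient rests largely on change within clusters at activation, adjusted for time. A pooled comparison of intervention with control patients mixes in differences between clusters and between calendar periods.
- **Lost precision.** A covariate that predicts the outcome but happens to be balanced is left out.
- **Open model.** With no threshold, two analysts can reach different primary models from the same data. Section 12.6.1 repeats the primary analyses in each subgroup without saying whether covariates are selected again there.

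**Working it through.** **1. The plan's own figure.** No figure in the plan depends on this rule. The only yardstick is the detectable effect of 0.048–0.055 SD in 12.2. Power, alpha and cluster-period sizes are not stated there, so it cannot be confirmed or called wrong. With 114,000 patients, 22 equal clusters, 6 periods, ICC 0.037 and a two-sided 5% test, the Hussey–Hughes variance gives 0.030 SD at 80% power and 0.034 SD at 90%. The stated range would correspond to about 33,000–43,000 analysed patients at 80% power, or 44,000–58,000 at 90%. It is used below for scale only.

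**2. What is fixed and what is selected.**

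| Always in the model | Enters only if imbalanced |
|---|---|
| Intervention, cluster intercept, constraint factors, calendar time, surgery type; baseline score in model (1) | Age, sex, race/ethnicity, insurance, rural residence, Elixhauser index; the two other baseline PROMIS scores, pain catastrophizing, TAPS item, PHQ-4, prior-year opioids |

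The right-hand column holds 6 + 6 = 12 factors for each PROMIS model. It assumes that the catastrophizing, TAPS and PHQ-4 items count as baseline measures; 13.1.2 gives them no time point.

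**3. Does the test see the relevant imbalance?** The simulation used 22 clusters, 6 periods and 114,000/(22 × 6) ≈ 864 patients per cell. The covariate shifts within clusters at activation and is tested at 5% with cluster-adjusted standard errors (21 df). The 5% level and the covariate ICC are assumptions; 0.037 is the ICC of the pain score in 12.2, borrowed for the covariate. Two independent runs gave these shares of shifts not flagged:

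| Shift | ICC 0.01 | ICC 0.037 | ICC 0.10 |
|---|---|---|---|
| 0.05 SD | not run | 74% | 87% |
| 0.10 SD | about 1% | 30–31% | 64–67% |

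On the same data, a contrast adjusted for cluster and period missed the 0.05 SD shift about 0.3% of the time. The information is in the data, but the planned test does not look for it.

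**4. Precision.** A second simulation had 600 replicates per scenario, 20 patients per cluster-period, outcome cluster variance 0.037/0.963 = 0.0384, and a prognostic covariate with no drift. The covariate was flagged in about 6% of trials, so it was left out in about 94%. Empirical SD of the effect estimate:

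- R² about 0.09: 0.0651 with imbalance testing, 0.0616 with a fixed list; ratio 1.057.
- R² about 0.20: 0.0662 against 0.0612; ratio 1.082.

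The closed form for the SE with the factor always included is √(1 − R²): 0.949 at R² = 0.10 and 0.894 at 0.20. Inverted, omission makes the SE 1/0.949 = 1.05 and 1/0.894 = 1.12 times as large. Each simulated SD has a relative Monte Carlo error of about 1/√(2 × 600) = 2.9%, so simulation and formula agree roughly. If the stated detectable effect scaled with the SE, R² = 0.10 would move it from 0.048–0.055 to 0.046–0.052 SD.

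**5. Data dependence of the model.** With 12 candidates and independent 5% tests, the chance that at least one enters by luck alone is 1 − 0.95¹² = 46%.

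**6. Type I error.** In the second simulation, with no drift or with linear drift of the covariate over calendar periods, the rejection rate under no effect was 0.04–0.07 for both approaches (Monte Carlo error about 0.01). These scenarios did not include a shift at activation.

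**7. Bias if such a shift occurs and is missed.** Bias = slope × shift. With a 0.10 SD shift and a standardised slope of 0.3–0.5, it is 0.3 × 0.10 = 0.03 to 0.5 × 0.10 = 0.05 SD. Neither the shift nor the slope comes from the documents.

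**The case against.** The strongest defence is that the plan already fixes what is likely to matter most. Cluster, constraint factors, calendar time, surgery type and the baseline PROMIS score are always adjusted for, and the remaining candidates form a closed pool named in advance. Enrolment is automatic with no exclusions (7.2, 7.3), which limits selection at recruitment, and the calendar-time term absorbs linear secular drift. All of this stands. It confines the point to the additional patient covariates, but it supplies neither a threshold nor a fixed list.

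A reader might infer three stronger things that the documents do not support.

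- **That the whole covariate set comes from the data.** It does not, for the reasons just given.
- **That the trial faces a bias about as large as its detectable effect.** The 0.03–0.05 SD figure needs an assumed shift at activation and applies only when the shift is missed. At covariate ICC 0.037, a 0.10 SD shift is flagged about 70% of the time. The slope must also hold after adjustment for baseline, surgery type and cluster; if standardised on the residual, 0.3–0.5 means one covariate explains 0.3² = 9% to 0.5² = 25% of residual variance. A shift among patients who return questionnaires is conceivable, since 8.4 expects some to be unable to complete them and 8.2 allows paper versions for some, but the documents do not show one.
- **That the testing inflates type I error.** The simulations showed no clear inflation.

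The defence is also right that a fixed list has a cost. Section 13.1.2 gives no time point for the pain catastrophizing scale. The surgery order triggers the message with the Guide, which addresses expectations about pain (8.1), so a score taken later could be a post-exposure variable. Section 12.5 has no rule for missing covariates, and forcing questionnaire items into every model could drop patients.

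**Conclusion.** The concern holds for the additional patient-level covariates. Section 12.5 selects them with a test that does not address the contrast being estimated, sets no threshold, and leaves out balanced prognostic factors. The demonstrable costs are discretion over the primary model and a standard error about 6–8% larger in simulation, under assumed R² of about 0.09–0.20 beyond the fixed terms. The gain is smaller if the fixed terms already explain most of what these covariates would. Bias from a missed case-mix shift remains a hypothetical illustration. This is a cheap improvement and does not show the planned analysis to be invalid.

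**What to change.** In both sentences of 12.5, replace the imbalance rule with a fixed list, in addition to the terms already mandatory: age, sex, race/ethnicity, insurance, rural residence, Elixhauser index and prior-year opioid prescriptions. Include pain catastrophizing only if it is measured before the Guide is sent. Define the opioid-history window so that it is pre-exposure and excludes discharge prescriptions, because 13.1.2 notes that these may be written before the procedure.

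State a simple rule for missing covariates so that no patient is dropped for that reason. Keep the balance table descriptive, and move any imbalance-driven adjustment to a sensitivity analysis. State that the subgroup analyses in 12.6.1 use the same list.

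The cost is a short edit, made before outcome data are analysed. The listed variables are already to be extracted under 13.1. The real work is the missing-covariate rule and confirming when the questionnaire items are collected.
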